4.2.2. Adverse events (AEs)

AEs

An adverse event refers to any untoward medical occurrence after subjects receive the investigational medicinal product, which can be manifested as symptoms, signs, diseases or laboratory test abnormalities, but are not necessarily related to the investigational medicinal product. See Section 10.1 of the protocol for details.

Treatment-emergent adverse event (TEAE)

TEAE is defined as an AE that occurs or worsens during treatment. The treatment period refers to the period from the first study drug administration to the end of the protocol-specified follow-up period. The cut-off date of TEAEs in Stage 1 is immediately before the first dose for Stage 2 or 10 weeks (70 days) after end of dosing in Stage 1, whichever occurs first; for the subjects who discontinue administration in Stage 1, the cut-off date of TEAEs is the end of follow-up period. TEAEs in Stage 2 is from the end of the first dose for Stage 2 to the end of the follow-up period.

Drug-related AEs

A drug-related AE refers to an AE whose relationship with the drug is related, possibly related or indeterminable.

The criteria for determination of the correlation of AEs with treatment are as follows:

Correlation	Criteria for determination
Related	
There is a reasonable temporal sequence between the occurrence of AE and the medication;The study drug explains the AE more reasonably than other reasons (e.g., the patient's preexisting disease, environmental or toxic factors, or other treatments the patient received, etc.);The AE disappears or lessens after the drug is stopped or the dose is reduced;The AE meets the known AE types of the suspect drug or its similar drugs;The AE recurs after re-administration.
Possibly related	
There is a reasonable temporal sequence between the occurrence of AE and the medication;The study drug explains the AE as reasonably as other reasons (e.g., the patient's preexisting disease, environmental or toxic factors, or other treatments the patient received, etc.);The AE disappears or lessens after the drug is stopped or the dose is reduced (if applicable).
Unlikely related	
Other reasons (e.g., the patient's preexisting disease, environmental or toxic

	
factors, or other treatments the patient received, etc.) explain the AE more reasonably than the study drug;
 
• The AE does not disappear or lessen after the drug is stopped or the dose is reduced (if applicable), or the situation is unclear;• The AE does not recur after re-administration, or the situation is unclear.
Not related	
• There is no reasonable temporal sequence between the occurrence of AE and the medication, or;• The AE has other evidence reasons (e.g., the patient's preexisting disease, environmental or toxic factors, or other treatments the patient received, etc.).
Indeterminable	
• The above information is unclear, and the investigator believes that it cannot be judged based on the existing information, and the investigator cannot obtain further follow-up information.

Serious Adverse Event (SAE)

An event will be considered an SAE if the following situations occur. See Section 10.1.2 of the protocol for definition of SAE. SAEs will be judged by investigators on CRF.

- Leading to death;
- Life-threatening: The investigator determines that the patient is at immediate risk of death when the event occurs. This definition does not include events that may lead to death if it is assumed to be more serious;
- Requiring hospitalization or prolongation of the original hospital stay;
- Leading to permanent or major disability or incapacitation (i.e., significant impairment of the subject's activities of daily living);
- Including congenital abnormalities or birth defects in the offspring of the patient;
- Significant medical events: According to the medical judgment of the investigator, other significant medical events that may endanger the patient and may require medical or surgical intervention to prevent one of the above outcomes.

Adverse Event of Special Interest (AESI)

AESIs in the study include: Conjunctivitis, keratitis, anaphylactic reaction, injection site reactions which persist over 24 h, AST/ALT increased $> 5 \times$ ULN, parasitic and opportunistic infection, pregnancy and symptomatic overdoses.

AEs leading to treatment discontinuation

In the study, action taken with study drug is drug discontinued or the subject will be withdrawn from treatment in response to these AEs.

4.2.3. Laboratory tests

Laboratory tests: Including hematology, blood biochemistry and urinalysis. The specific assessments are shown in Table as follows:

Table 3: Laboratory tests

Hematology	Blood biochemistry	Urinalysis
White blood cell count	Sodium	Bilirubin
Hemoglobin	Potassium	Red blood cells
Hematocrit	Calcium	White blood cells
Red blood cell count	Chlorine	Glucose
Platelet count	Serum urea/urea nitrogen	Ketone
Neutrophil percentage	Creatinine	Nitrite
Lymphocyte percentage	Glucose	pH
Monocyte percentage	Total protein	Protein
Basophil percentage	Albumin	Urine specific gravity
Eosinophil percentage	Total bilirubin	Urobilinogen
Absolute neutrophil count	Alanine aminotransferase	Microscopic examination (if necessary)
Absolute lymphocyte count	Aspartate aminotransferase	
Absolute monocyte count	γ -glutamyltransferase	
Absolute eosinophil count	Alkaline phosphatase	
Absolute basophil count	Lactate dehydrogenase	
	Creatine phosphokinase	
	Total cholesterol	
	Low-density lipoprotein	
	High-density lipoprotein	

4.2.4. Electrocardiogram (ECG)

12-lead ECG will be performed to collect ventricular rhythm, PR, QRS, QT, and QTcF.

4.2.5. Others

Vital signs

Vital signs include systolic and diastolic blood pressure, heart rate, body temperature, and respiratory rate.

Physical examination

Physical examination includes general appearance, skin, eyes/ears/nose/throat, head and neck, cardiovascular system, respiratory system, abdomen, limbs, lymph nodes, musculoskeletal and nervous systems. Unless it is necessary to assess the status of AD involvement, there is no need to perform rectal or genital examinations.

Other tests

ADA test.

4.3. PK/PD Endpoints

PK endpoints: To analyze the blood concentration of CBP-201, and calculate the PK characteristics at steady-state trough concentrations of individuals and each group of subjects at each treatment time point.

PD endpoints: Change in serum IL-4, IL-13, IgE, TARC levels and peripheral blood eosinophil count from baseline.

5. Statistical Hypothesis

The primary efficacy endpoint of the study is the proportion of subjects whose IGA score is 0-1 and decreased by ≥ 2 points from baseline at W16. The following null and alternative hypotheses will be evaluated by statistical tests based on the efficacy endpoint. A two-sided significance level of 5% ($\alpha = 0.05$) will be adopted. If p value is ≤ 0.05 , the null hypothesis will be rejected and it is considered that there is a statistically significant difference in IGA parameter between the CBP-201 300 mg Q2W group and the placebo group.

Null hypothesis (H0): Efficacy in the CBP-201 300 mg Q2W group = efficacy in the placebo group

Alternative hypothesis (H1): Efficacy in the CBP-201 300 mg Q2W group \neq efficacy in the placebo group

6. Analysis Datasets

The primary analysis of the study will be performed based on the data of Stage 1, that is, placebo-controlled stage. The data of primary analysis will include all Stage 1 data from the 255 subjects who are enrolled in accordance with V2.1 and its earlier versions of the protocol. After the 255 subjects enrolled based on the V2.1 and its earlier versions of the protocol complete the treatment, related evaluations and follow-up of Stage 1 (W16 pre-dose visit), the primary analysis will be performed based on the data of the 255 subjects.

The analyses for Stage 2 will still be based on the data from 255 subjects who are enrolled in accordance with V2.1 and its earlier versions of the protocol. The data analyzed for Stage 2 will include all data from the 255 subjects who are enrolled in accordance with V2.1 and its earlier versions of the protocol that are collected from the start of Stage 2 to the end of study. After all subjects who enter Stage 2 (including the 75 subjects newly enrolled) have completed treatment, evaluation and follow-up, the analyses for Stage 2 will be performed based on the data from 255 subjects who are enrolled in accordance with V2.1 and its earlier versions of the protocol.

Supplementary analysis will include all subjects (including the 75 subjects newly enrolled). The same analysis method as that for the primary analysis and Stage 2 analysis will be used.

The following 6 analysis datasets will be included in the primary analysis.

Screening set 1

It will include all subjects who have signed the informed consent form.

Randomization set 1 (RS1)

RS1 will include all subjects who have been randomized at baseline (D1), regardless of whether they have received the study drug.

Full analysis set 1 (FAS1)

FAS1 will include all subjects who have been randomized and received at least one dose of the study drug. Subjects are analyzed within FAS1 according to treatment assigned.

Per protocol set 1 (PPS1)

PPS1 will include all subjects in FAS1 without any major protocol deviation that affects efficacy analysis. Major protocol deviations that affect efficacy analysis have been discussed and determined at the blinded data review meeting for the primary analysis of the study on September 19, 2022, and have been discussed and determined again at the blinded data review meeting for the final analysis of the study on October 18, 2023. Minutes of the data review meeting will be presented in an annex.

By far, protocol deviations that affect efficacy analysis of the 255 subjects in Stage 1 are due to the following causes:

1. Missing doses (I. Missing W12 and W14 doses; II. Missing 3 doses in Stage 1, equivalent to a compliance with study drug lower than 70%);
2. Missing key efficacy results at W16 (both IGA and EASI missing);
3. Key efficacy results at W16 out of window (both IGA and EASI out of window >10 days);
4. Incorrect stratified randomization (only Stage 1);
5. Violation of inclusion or exclusion criteria (topical corticosteroids are used before baseline; baseline disease severity fails to meet the requirements);
6. Prohibited drugs (non-rescue treatment) that may affect efficacy

Safety set 1 (SS1)

SS1 will include all randomized subjects who have received at least one dose of study drug. Subjects are analyzed within SS1 according to the treatment they actually received.

PK set 1 (PKS1)

PKS1 will include subjects who have received at least one dose of CBP-201 active drug and had at least 1 collected and analyzable PK sample.

The Stage 2 analysis will be defined as the following analysis populations.

Randomization set 2 (RS2)

RS2 will include all subjects who have been randomized to Group C or D and all subjects assigned to Group E.

RS2_R: RS2_R will include all subjects who have been randomized to Group C or D.

RS2_NR: RS2_NR will include all subjects who have been assigned to Group E.

Full analysis set 2 (FAS2)

FAS2 will include all subjects who have been randomized to Group C or D and all subjects who have been assigned to Group E and received at least one dose of the study drug in Stage 2. Subjects are analyzed within FAS2 according to treatment assigned.

FAS2_R: FAS2_R will include all subjects who have been randomized to Group C or D and received at least one dose of the study drug for Stage 2.

FAS2_NR: FAS2_NR will include all subjects who have been assigned to Group E and received at least one dose of the study drug for Stage 2.

Safety set 2 (SS2)

SS2 will include all subjects in RS2 who have received at least one dose of the study drug for Stage 2. Subjects are analyzed within SS2 according to the treatment they actually received.

Safety set 3 (SS3)

SS3 will include all subjects in SS1 and SS2 who have received at least one dose of the study drug.

PK set 2 (PKS2)

PKS2 will include all subjects who have received at least one dose of CBP-201 active drug for Stage 2 and have at least 1 collected and analyzable PK sample for Stage 2.

For the supplementary analysis based on all subjects (including the 75 subjects newly enrolled), the definitions of analysis sets are the same as above.

Table 4: Analysis Population, Treatment Group and Analysis Stage

Analysis Populations	Treatment Groups	Analysis Stage
RS1/ FAS1/ PPS1/ SS1	1) Placebo 2) CBP-201 300 mg Q2W	Stage 1 treatment period.
RS2_R/ FAS2_R	1) Placebo/CBP-201 300 mg Q2W 2) Placebo/CBP-201 300 mg Q4W 3) CBP-201 300 mg Q2W/CBP-201 300 mg Q2W 4) CBP-201 300 mg Q2W/CBP-201 300 mg Q4W 5) Q2W Total 6) Q4W Total 7) Total	From the completion of Stage 2 randomization to the end of study for subjects who have completed Stage 1 and been randomized to Group C or D.
RS2_NR/ FAS2_NR	1) Placebo/CBP-201 300 mg Q2W 2) CBP-201 300 mg Q2W/CBP-201 300 mg Q2W 3) Open-Label Q2W Total	From the start of Stage 2 to the end of study for subjects who have completed Stage 1 and been assigned to Group E.
SS2	1) CBP-201 300 mg Q2W (Group C) 2) CBP-201 300 mg Q4W (Group D)	From the first dose for Stage 2 to the end of Stage 2.

	3) CBP-201 300 mg Q2W (Group E) 4) Total	
SS3	1) CBP-201 300 mg Q2W 2) CBP-201 300 mg Q2W/CBP-201 300 mg Q4W 3) CBP-201 300 mg Q2W/CBP-201 300 mg Q4W/CBP-201 300 mg Q2W 4) CBP-201 300 mg Q4W 5) CBP-201 300 mg Q4W/CBP-201 300 mg Q2W 6) Total	It includes all subjects who have received at least one dose of CBP-201 from Stage 1 to Stage 2. From the first dose of CBP-201 to the end of study.

7. Statistical Methods

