- PK set 2 (PKS2) will include subjects who have received at least one dose of CBP-201 active drug in Stage 2 and had at least 1 collected and analyzable PK sample.

At stage 2, for subjects in group C or group D who have not achieved EASI-50 and are therefore assigned to group E to receive subcutaneous injection of CBP-201 300 mg every 2 weeks, their

efficacy variables and safety variables will be analyzed by assigned treatment groups or actual treatment groups and by stages.

The detailed definition of the statistical analysis data sets will be supplemented or adjusted in the SAP.

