7.5.2. AEs

AEs will be analyzed based on the SS1 and SS2. Subjects who have received at least one dose of the study drug will be analyzed based on SS3.

AEs will be coded using MedDRA.

The occurrence of overall AEs will be summarized to generate summary tabulations of TEAEs. TEAEs of special interest and drug-related AESIs will be summarized. The numbers of subjects with various AEs, numbers and incidences of events will be calculated. The number of subjects with various AEs, the number of events, the incidence and annual incidence of events will be calculated based on SS3.

AEs, drug-related AEs, SAEs, AESIs, AEs leading to death, AEs leading to treatment discontinuation, injection site AEs, CTCAE grade 3-5 AEs, AEs with an incidence of $> 5\%$, and AD recurrence-related AEs will be tabulated.

The incidences of the following TEAEs will be summarized by SOC and PT, the numbers of subjects with various AEs, and the numbers and incidences of events will be calculated. They will be ranked in descending order of total number of subjects by SOC and PT. In addition, annual incidences of TEAEs, treatment-emergent SAEs, treatment-emergent AESIs, drug-related AEs, drug-related SAEs will be calculated by SOC and PT based on SS3.

- 1) TEAEs;
- 2) Drug-related AEs;
- 3) SAEs;
- 4) Drug-related SAEs;
- 5) AEs leading to death;
- 6) AEs leading to treatment discontinuation;
- 7) AEs leading to treatment interruption;
- 8) AESIs;
- 9) Drug-related AESIs;
- 10) Injection site AEs;
- 11) CTCAE grade 3-5 AEs;
- 12) AEs with an incidence of $> 5\%$;

In addition, the incidences of TEAEs, AESIs, and injection site AEs will be summarized by CTCAE Grade, correlation with study drug, SOC and PT, and the number and percentage of subjects will be calculated.

A subject with an AE of the same SOC and PT more than once will have that event counted only once within each SOC and PT.

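### SS3 adverse-event rates are tabulated by the regimen sequence a subject later received, so three of the five columns contain time in which an AE could not have stopped treatment

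*SAP*

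**What the plan says.** The later SAP (the version that covers Stage 2), section 6, Table 4, gives SS3 five regimen columns plus a total. They are Q2W; Q2W/Q4W; "3) CBP-201 300 mg Q2W/CBP-201 300 mg Q4W/CBP-201 300 mg Q2W"; and, for subjects on placebo in Stage 1, "4) CBP-201 300 mg Q4W 5) CBP-201 300 mg Q4W/CBP-201 300 mg Q2W". The analysis period for that row is "From the first dose of CBP-201 to the end of study". SAP 7.5.2 then says that the "incidence and annual incidence of events will be calculated based on SS3". No text allocates SS3 events or person-time to the regimen in force at onset, and the denominator of annual incidence is not defined.

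SS2 has columns for Groups C, D and E and a total, over the period "From the first dose for Stage 2 to the end of Stage 2". Its grouping rule is "Subjects are analyzed within SS2 according to the treatment they actually received". Nothing is said about a subject who receives two regimens within Stage 2. Protocol 12.4 says that the efficacy and safety variables of subjects moved to Group E "will be analyzed by assigned treatment groups or actual treatment groups and by stages", and leaves the detail of the analysis sets to the SAP.

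Across W16 the SAP does separate events. Under 4.2.2, Stage 1 TEAEs stop no later than just before the first Stage 2 dose, and Stage 2 TEAEs start there.

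**The concern.** A sequence label is known only after the last switch, but the SS3 clock starts at the first CBP-201 dose. Two things follow.

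- **Guaranteed time.** A Group A subject can be labelled Q2W/Q4W only by still being on treatment at W16. No AE can have ended treatment in those 16 weeks, yet the weeks enter the denominator. The Group A subjects whom an AE did stop in Stage 1 have received Q2W only, so they are counted in the Q2W column. Columns 3 and 5 have the same feature up to the move to Group E.
- **Mixing.** AEs that arose on Q2W in Stage 1 are counted under a sequence label that contains Q4W.

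SS3 is the long-term safety summary, and its columns will be read side by side. Q2W/Q4W could look better tolerated than Q2W for AEs leading to discontinuation when the two regimens are the same. For other AEs, a real difference would be diluted.

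**Working it through.** The documents give no figure for this, so there is nothing of the plan's own to reproduce.

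**Inputs from the documents**
- Q4W starts at W16, only for EASI-50 responders, randomised 1:1 to C or D (SAP 3.1).
- A move to E needs two consecutive failed EASI-50 assessments (SAP 3.1). Stage 2 investigator assessments are every 4 weeks from W20 (protocol 6.2.3.2). The earliest move is therefore W24, and the latest at a dosing visit is W48.
- Exposure is last dose minus first dose plus 14 days (SAP 4.2.1). With the last dose at W50, a full course is 52 weeks from Day 1 or 36 weeks from W16.
- 170 and 85 subjects randomised (SAP 3.2).

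**Assumptions not in the documents:** a constant discontinuation-AE hazard λ per week, equal on both regimens; rare events; W16 EASI-50 of 60-80% on CBP-201 and 30-50% on placebo; 10% or 20% of Group D moving to E, spread evenly over W24-W48.

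**Step 1. Guaranteed time as a share of a full course**
- Column 2 (Q2W/Q4W): 16/52 = 30.8%
- Column 3 (Q2W/Q4W/Q2W): at least 24/52 = 46.2%, up to 48/52 = 92.3%
- Column 5 (Q4W/Q2W): at least 8/36 = 22.2%, up to 32/36 = 88.9%
- Column 4 (Q4W after placebo): 0/36 from Stage 1

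**Step 2. Discontinuation AEs, ignoring moves to E**
- Column 2 rate: 36λ/52 = 0.69λ.
- Q2W column at EASI-50 60%/30%: 51 + 68 = 119 Group A subjects and 12.75 + 59.5 = 72.25 Group B subjects enter C or E. Events are 170×16λ + (119 + 72.25)×36λ = 9,605λ. Person-weeks are 119×52 + 72.25×36 = 8,789. The rate is 1.09λ.
- Q2W column at 80%/50%: 102 and 63.75 subjects, 8,687λ over 7,599 person-weeks, or 1.14λ.
- Q2W/Q4W therefore shows 0.61-0.63 of the Q2W rate (Q2W appears 1.58-1.65 times higher). If person-time runs to W60 with events only on treatment, Q2W appears 1.55-1.62 times higher.

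**Step 3. Allowing moves to E**
- The mean move is at W36, 20 weeks after W16. With 10% moving, column 2 has (0.9×36 + 0.1×20)λ = 34.4λ events over about 0.9×52 = 46.8 weeks, or 0.74λ. With 20% moving, it has 32.8λ over 41.6 weeks, or 0.79λ.
- At EASI-50 80%/40%, the Q2W column is 8,840λ over 7,752 person-weeks, or 1.14λ. The ratios are 0.64 and 0.69.
- A simulation of 200,000 subjects, with hazards of 3, 6 and 12 per 100 patient-years, gave 0.63-0.69. At a true 6 per 100, the Q2W column showed 6.81 and Q2W/Q4W showed 4.39-4.69.
- With 10% moving and a true Q4W hazard 1.5 times that of Q2W (6 per 100), the columns showed 6.57 against 6.81, a ratio of 0.96.

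**Step 4. Events counted under the regimen at onset.** The same simulated data gave 5.96 on Q2W and 5.97-5.99 on Q4W for a true 6 on both. They gave 5.96 and 9.00 when the true ratio was 1.5. The recovery depends on the constant hazard built into the simulation.

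**Step 5. Other AEs.** If the true Q4W:Q2W rate ratio is R, the Q2W/Q4W column shows (16 + 36R)/52 relative to Q2W. R = 1.5 shows as 70/52 = 1.35, and R = 2.0 as 88/52 = 1.69.

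**The case against.** The best defence is that the regimen comparison belongs in SS2, not SS3. Groups C and D are randomised at W16 and both are counted from the first Stage 2 dose, so survival through Stage 1 cannot favour one over the other. The SS3 columns are openly labelled as sequences. Stage 2 has no inferential testing, and no study objective names a Q2W versus Q4W safety contrast. The list in SAP 7.5.2 of AE classes annualised by SOC and PT omits AEs leading to discontinuation. All of this stands, and it limits the point to how descriptive tables are read. It does not remove the point: the SS3 overview sentence covers annual incidence of AEs generally, AEs leading to discontinuation stay in the SOC/PT incidence list, and no planned table gives SS3 rates by regimen at onset.

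A reader might infer three stronger points. The documents do not support them.
- **That SS2 locks a switcher into one group.** It states no rule for a D-to-E subject, and counting by treatment at onset is one possible reading of its text. The fault is a missing rule. Subjects moved from C to E stay on 300 mg Q2W, so their regimen is not misattributed.
- **That AEs are never split by regimen at onset.** SS1 and SS2 do split them at the first Stage 2 dose.
- **That every Q4W column has guaranteed time.** Column 4 starts at W16 with none from Stage 1. Its simulated rate (6.24-6.66 against a true 6) is slightly raised because subjects who reach a switch leave for column 5.

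A further fair objection is that rates by regimen at onset are not a clean comparison either. Q2W time would hold all Stage 1 active exposure and the Group E non-responders, and Q4W time only W16 responders. Carry-over blurs the switch: protocol 4.4.1 reports drug detectable to a median of 56 days after a single 600 mg dose. The new table should therefore supplement the sequence columns, not replace them.

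**Conclusion.** The point holds for SS3 columns 2, 3 and 5. The guaranteed-time shares follow from the visit schedule and exposure formula alone. The size of the distortion is an illustration. With equal constant hazards and the assumed response and switching rates, Q2W/Q4W shows about 0.63-0.69 of the Q2W rate of AEs leading to discontinuation, or 0.61-0.63 if nobody moves to E. Put the other way, Q2W appears about 1.45-1.65 times higher when the truth is 1.0. For other AEs the effect is dilution through the 16 weeks of Q2W in a 52-week course. In SS2 the gap is one unstated rule. No hypothesis test, and no randomised C versus D contrast, is affected by survival through Stage 1.

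**What to change.** - In SAP 7.5.2, keep the SS3 sequence columns and add one SS3 table with AE counts and person-years allocated to the regimen in force at AE onset (Q2W or Q4W). Define the person-time denominator there.
- Footnote that table as descriptive and non-randomised, because Q2W time includes all Stage 1 active exposure and EASI-50 non-responders.
- Say that the Q2W versus Q4W safety reading is taken from randomised Groups C and D in SS2.
- In section 6 (SS2), state how D-to-E subjects are handled. One option is to show C and D as randomised, with events after reassignment to E also shown separately. This keeps the randomised contrast intact and settles the choice that protocol 12.4 leaves open.

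The cost is SAP wording and one extra table. AE start dates and study drug administration are already recorded (protocol 10.4.1 and 13.7). The remaining weakness is that rates by regimen at onset stay confounded with time on study and response status, with carry-over around each switch.
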